### 10.2 Planned recruitment rate

With the anticipated support of up to 120 centres/sites within the UK, the logarithmic decay model predicts that the required number of patients will be recruited by March 2014 (assuming follow-up until March 2016).

The trial manager and trial co-ordinators will continue to provide support to their respective recruitment centres and the relevant research nurses employed through the CLRN and other mechanisms.

The trial will continue to be publicised through the AR UK's "Arthritis Today" magazine and through the National Rheumatoid Arthritis Society (NRAS) as well as local resources. A British Society for Rheumatology (BSR) special interest group has been set up to act as a forum for the study investigators and TRACE RA news are regularly discussed in the quarterly BSR leaflet. A TRACE RA website has also been established.

### 10.3 Compliance

Compliance will be estimated based on patient reports on Case Report Forms and patients will be considered compliant if they report taking 'most' of their study tablets since their last visit. In addition, the difference in LDL cholesterol will be measured in a random sample of 400 participants in June 2011 and at intervals during the trial to allow the average difference in LDL to be estimated.

### 10.4 Planned analyses

All patients randomised will be included in the analysis, irrespective of whether the study drug is continued (ITT analysis). Cox regression models will be developed for time to occurrence of a first cardiovascular event or serious adverse event using treatment allocation as the independent variable.

The models will be adjusted for factors used in the stratification (centre) and for any baseline imbalances. However, the trial is of sufficient size to expect that most potential confounders (e.g. smoking, aspirin, NSAID/Coxib, corticosteroid, anti-TNF usage etc) are likely to be balanced between the groups. Treatment differences will be expressed as hazard ratios with 95% confidence intervals. Two-sided p values of  $\leq$ 0.05 will be considered significant.

Kaplan-Meier Product Limit (PL) estimates of the survival curves with 95% confidence intervals will be calculated.

### Analysis of rheumatology outcomes

All patients randomised in the TRACE RA DAS substudy trial will be included in the analysis, irrespective of whether the study drug is continued (intention-to-treat analysis). The dependent variable will be the

dichotomous variable of EULAR response. Any further baseline variables can be incorporated into the model if necessary to adjust for baseline imbalances. Treatment differences will be expressed as odds ratios with 95% confidence intervals. Two-sided p values of  $\leq 0.05$  will be considered significant.

### 10.5 Procedure for accounting for missing data

Tests will be conducted to explore whether missing data are missing at random and appropriate procedures then deployed to impute the missing data.

### 10.6 Planned sub-group analyses

Sub-group analyses will be carried out with respect to: sex; age ( $\leq 65$  vs. >65 years); RA disease duration; rheumatoid factor status and anti-TNF therapy (if numbers are sufficient). It is recognised that these subanalyses will have less statistical power than those based on the whole study sample and this will be reported appropriately.

### 10.7 Interim analyses and its frequency

Interim analyses will be performed when the number of events reaches 25%, 50% and 75% of the total expected events. No formal stopping rule will be set but the DMC will advise the Chairman of the Trial Steering Committee that the trial should be stopped if, in DMC's view, the randomised comparison in the trial has provided both (a) proof beyond reasonable doubt that for all, or for some, types of patients the trial treatment is clearly indicated or clearly contraindicated in terms of a net difference in major morbidity and mortality, and/or (b) evidence that might reasonably be expected to influence the patient management of clinicians aware of the results of any other studies. Safety data will be continuously monitored by the independent DMC.

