### 12.8 Ethical considerations

The original trial protocol was submitted for ethical review to COREC. The MREC ref no is 06/Q1704/171. The trial did NOT commence recruitment until central (MREC & MHRA) and individual site (SSI & R&D) regulatory approvals were in place at each recruiting centre. Any subsequent amendments (including this revised protocol) will be submitted to the same MREC and will not be implemented until approval has been received and notified to all participating sites.

The main ethical consideration pertaining to the TRACE RA trial is whether the trial should be terminated early if efficacy of atorvastatin is proven. The planned interim analyses should ensure that the trial continues only as long as is needed to establish, beyond reasonable doubt, that treatment with atorvastatin is either beneficial or harmful to patients with RA.

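### Protocol 10.7 makes its two stopping criteria both jointly required and separately sufficient; the looser reading conflicts with 12.8

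*Protocol*

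**What the plan says.** Section 10.7 fixes the timing of the looks: "Interim analyses will be performed when the number of events reaches 25%, 50% and 75% of the total expected events". It then sets out how the DMC is to act: "No formal stopping rule will be set but the DMC will advise the Chairman of the Trial Steering Committee" that the trial should stop if, in the DMC's view, certain conditions hold.

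The conditions come in one sentence. It opens with "the randomised comparison in the trial has provided both (a) proof beyond reasonable doubt that for all, or for some, types of patients" the treatment is clearly indicated or contraindicated, judged on net major morbidity and mortality. It continues with "and/or (b) evidence that might reasonably be expected to influence the patient management of clinicians aware of the results of any other studies". The section ends by giving the DMC continuous oversight of safety data.

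Section 12.8, on ethics, treats early termination as the main issue. The purpose it gives for the interim looks is a study that "continues only as long as is needed to establish, beyond reasonable doubt, that treatment with atorvastatin is either beneficial or harmful".

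Section 10.4 sets the final criterion: two-sided p values up to "0.05 will be considered significant". No allowance for the interim looks is mentioned.

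**The concern.** The sentence in 10.7 is the only statement in the protocol of when the DMC should advise stopping, and it cannot be followed as written. *Both* makes (a) and (b) joint requirements. *And/or* makes either enough.

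Criterion (a) carries a demanding standard of proof. Criterion (b) carries none: it asks only whether the evidence might influence practice. A DMC member who relies on *and/or* could properly recommend stopping for benefit on evidence well short of what 12.8 describes. A member who relies on *both* could not.

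At stake is how much protection the final test has. Three earlier looks cost almost nothing in type I error if stopping for benefit needs very strong evidence. They cost a good deal if ordinary significance is enough.

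**Working it through.** **1. The texts side by side**

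| Place | What it requires before stopping |
|---|---|
| 10.7, governed by *both* | (a) and (b) together |
| 10.7, governed by *and/or* | (a) alone, (b) alone, or the two together |
| 12.8 | Benefit or harm established beyond reasonable doubt, the standard found in (a) |

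The joint reading of 10.7 satisfies 12.8, because (a) is always met. Stopping on (b) alone does not. So 10.7 contradicts itself, and one of its two readings also contradicts 12.8.

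**2. What depends on the choice**

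The protocol gives no error rate for its interim scheme, so there is no figure of its own to reproduce. It also gives no p value for (a) or (b), so the interim threshold below is an assumption and is varied.

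Inputs from the protocol:
- looks at information fractions t = 0.25, 0.50 and 0.75 (10.7), plus the final analysis at t = 1;
- final two-sided level 0.05 with no adjustment (10.4), so the final critical value is 1.960.

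Method. Under no treatment effect, the score process B(t) has independent normal increments, each with variance 0.25 between successive looks. The test statistic is Z(t) = B(t)/√t. For an assumed interim p threshold with critical value c, the trial is counted as falsely positive if |Z(0.25)|, |Z(0.50)| or |Z(0.75)| exceeds c, or if |Z(1)| exceeds 1.960. Benefit-direction error counts only trials whose first crossing favours atorvastatin; its nominal value is 0.05/2 = 2.5%. The results come from 4 million simulated null paths. They depend on the information fractions, not on the event total.

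| Assumed interim threshold | c | Any interim crossing | Overall two-sided error | Benefit direction |
|---|---|---|---|---|
| p<0.05 | 1.960 | 10.7% | 12.6% | 6.3% |
| p<0.01 | 2.576 | 2.4% | 6.2% | 3.1% |
| p<0.005 | 2.807 | 1.2% | 5.5% | 2.8% |
| p<0.001 | 3.291 | 0.26% | 5.1% | 2.5% |

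**3. Reading the table**

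If (a) must always be met and is taken to mean something like p<0.001, the unadjusted final 0.05 is nearly harmless. The excess is 5.1% − 5.0% = 0.1 percentage point, and a final level of about 0.049 would remove it. If (b) alone were enough and were met by nominal significance at every look, overall error would be 12.6/5.0 ≈ 2.5 times nominal. The wording of 10.7 decides which end of the table is relevant.

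**The case against.** The best defence is that this is a drafting slip that an experienced DMC would read sensibly. *Both* supports the joint reading as much as *and/or* opposes it, and 12.8 points the same way. The DMC only advises, and the steering committee considers its advice. This stands as far as it goes: the documents do not show that (b) alone is the intended rule. It does not remove the contradiction, because 10.7 is the guidance the DMC is given.

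A reader might be tempted to go further in four ways, none of which the documents support.

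- *That the trial's type I error is 12.6%.* That figure needs the DMC to advise stopping at any p<0.05 at every look, which no section says. It also counts both directions; only about half concerns a false claim of benefit.
- *That (b) is easily met because statins already work in other populations.* Section 10.7 requires the evidence to come from this trial's randomised comparison and to matter to clinicians who already know the other results. Results from elsewhere do not by themselves satisfy (b).
- *That the missing boundary is itself an error.* Declining a formal rule is a stated choice. Appendix 11.1 records that a p-value guide was removed because it could be misread. Appendix A9.3 calls for a detailed interim analysis plan that satisfies the DMC; it is not shown and may hold such detail.
- *That swapping* and/or *for* and *leaves harm untouched.* Criterion (a) covers contraindication as well as indication, so a bare substitution would bind recommendations on harm too. The fix has to deal with this.

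**Conclusion.** The point holds as an internal contradiction in the DMC's only stated stopping criteria, one reading of which conflicts with 12.8. It is worth correcting because the protocol has no numerical boundary and no final adjustment to limit the looser reading.

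The numerical consequence is a range, not an estimate: from about 5.1% overall two-sided error at an assumed interim p<0.001 to 12.6% in the assumed worst case, with about 2.5% to 6.3% in the benefit direction. This rests on looks at exactly the planned fractions, a normally distributed test statistic with independent increments, and a fixed p threshold standing in for a DMC judgement that would in practice be broader. The textual contradiction rests on none of these assumptions.

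**What to change.** In 10.7, replace *and/or* with *and*, so that an interim recommendation to stop for efficacy requires (a) and (b) together and agrees with 12.8. Add a sentence saying that this requirement does not restrict the DMC's continuous safety monitoring or its judgement on harm. Since 12.8 now applies one standard to benefit and harm alike, carry the same qualification there so that the two sections stay consistent.

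A numerical guide for benefit, such as p<0.001 on the primary endpoint, is optional. It is a trade-off against the sponsor's deliberate choice to set no formal rule. If wanted, it belongs in the interim analysis plan agreed with the DMC under Appendix A9.3, worded as necessary but not sufficient for stopping. With it, the final 0.05 could stand practically unchanged.

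The cost is a word and a sentence in 10.7, a matching phrase in 12.8, and the same wording in the DMC's own papers. The one real downside is a little less freedom to stop early on moderate evidence of benefit, which 12.8 already implies.

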### 10.8 Economic analyses

The trial will not address any economic issues directly but, since EQ5D can be used for health utility assessment [75], the results can subsequently be used for economic modelling and cost-effectiveness based on calculation of QALYs gained.

The trial will also monitor the number of hospital admissions and length of stay that occur via information collated from the CRFs.

### 11. ASSESSMENT OF EFFICACY AND SAFETY

### 11.1 Assessment of efficacy outcomes

The records of English and Welsh randomised patients' will be electronically tagged for mortality with the Office for National Statistics (ONS) and Scottish patients at the Scottish Office's Information and Statistics Division (ISD) as well as the local hospital Trusts' Medical Information departments. Underlying cause of death will be ascertained from death certificates provided by ONS and ISD (which also supply details of times and causes of all hospital admissions in Scotland) supplemented by information from hospital records, including post-mortem examinations, if performed.

Hospital admissions will be ascertained at each centre by matching the patient details with national NHS Hospital Episode Statistics. In addition, non-fatal events will be ascertained regularly by contact with each patient. If necessary additional information will be sought from household members, GP or hospital departments.

### 11.2 Assessment of safety

Statin safety-related outcomes, as stated in Appendix 6, will be monitored by the independent DMC. The only 2 recognised adverse effects of atorvastatin are:

- Myopathy (muscle pain or weakness in association with a raised CK>10x ULN); and
- Liver function abnormalities

These will be monitored at each follow-up by reviewing ALT or AST results and asking about new and significant muscle symptoms.

### In the presence of new and significant muscle symptoms:

(a) If CK>10xULN, then stop trial medication - not to be restarted.

(b) If ALT/AST<2xULN and CK are <3xULN, trial medication can be continued with clinical follow-up. Further measurements of ALT/AST and CK can be requested if thought to be necessary by managing rheumatologist.

(c) If ALT/AST >2xULN and/or CK between 3-10xULN retest in 1-2 weeks: (c1) if normalisation has occurred to ALT/AST<2xULN and CK<3xULN then act as per option (b) above; (c2) if CK>10xULN stop trial medication; (c3) if ALT/AST>2xULN and CK again between 3-10xULN retest in 1 week: if elevation persists then stop trial medication.

### In the absence of any new and significant muscle symptoms:

In general, if abnormalities of LFTs with atorvastatin are to occur, they are more likely to occur within the first 3-6 months of treatment. After that, any DMARD or non-steroidal therapy (or other medications) would be a more likely cause of LFT abnormalities and the managing rheumatologists should consider stopping these drugs prior to stopping the trial medication. Attribution of LFT abnormalities to the trial medication or anti-rheumatic drug is left to the managing rheumatologist, but the TRACE RA team, including the Chief and Lead Investigators or delegated person could advise, if necessary.

# If LFT abnormalities are thought to be attributable to anti-rheumatic medication rather than trial **drug:** then follow usual rheumatology practice guidelines (e.g. BSR monitoring guidelines).

### If LFT abnormalities are thought to be attributable to trial drug rather than other reasons:

(a) If ALT/AST within normal range or <2xULN, then continue trial medication and arrange next follow-up.

(b) If ALT/AST between 2-3xULN then continue trial medication and retest in 1 week. (b1) if normalisation to <2xULN has occurred, then act as per option (a) above. (b2) if ALT/AST persists at between 2-3xULN or more, then temporarily stop trial medication and act as per option (c) below.

(c) If ALT/AST>3xULN continue trial medication and retest one week later: (c1) if ALT/AST has recovered to <2xULN then continue trial medication and act as per options (a) above; (c2) if ALT/AST between 2-3xULN then retest in 1 week and if ALT/AST persists at between 2-3xULN or more, temporarily stop trial medication and act as per option (c3); (c3) if ALT/AST elevation persists at >3xULN then temporarily stop trial medication and retest in 3 weeks: (c3i) if normalisation has occurred, then act as per options (a) or (b), whichever applies; (c3ii) if abnormality persists at >3xULN then stop trial medication – not to be restarted.

# **12. RESEARCH GOVERNANCE**

### 12.1 Trial administration and logistics

Dudley Group of Hospitals NHS Foundation Trust and the University of Manchester are co-sponsors of the TRACE RA trial. Sponsorship activities and delegated responsibilities are shared between Dudley Group of Hospitals NHS Foundation Trust, the employer of the Chief Investigator (CI); and the University of Manchester, in accordance with the UK Medicines for Human Use (Clinical Trials) Regulations 2004 and in line with the Research Governance Framework for Health and Social Care, April 2005 2nd Edition, and according to ICH GCP. Both parties agree to allow inspection of sponsors' premises by the competent authorities.

### Dudley Group of Hospitals NHS Foundation Trust (DGOH) & Chief Investigator responsibilities:

- Put and keep in place arrangements to adhere to ICH GCP
- Ensure that Investigational Medicinal Products (IMPs) are made available to subjects free of charge
- Take appropriate urgent safety measures
- Ensure that Pharmacovigilance is maintained throughout the duration of the trial please note that the administration of Pharmacovigilance for the trial has been delegated to the University of Manchester by the Chief Investigator.
- Ensure that PIs conduct the study in accordance with ICH GCP, the DOH Research Governance Framework and laws and statutes that relate to the study and any local requirements as may be specified by their host institution.
- Responsibility for putting and keeping in place arrangements to conduct the study according to Good Clinical Practice, the DOH Research Governance Framework and the laws and statutes that relate to the study
- Responsibility to use all reasonable efforts to ensure that the data collected and reported are accurate, complete and identifiable at source; and that record keeping and data transfer procedures adhere to the Data Protection Act 1998.
- Responsibility for monitoring the study in accordance with the arrangements outlined in the submission to the Sponsor.
- Responsibility to supply documentation and reports as deemed necessary by the Sponsor to fulfil its obligations.
- Responsibility to co-operate with audits or inspections undertaken by the host institution, the Sponsor and regulatory authorities, including the MHRA, as required.
- Responsibility to assist investigations into any alleged research misconduct undertaken by or on behalf of the Sponsor.
- Responsibility to make the necessary provision for archiving essential documents.

### AR UK Epidemiology Unit, University of Manchester responsibilities:

Trial Administration Responsibilities:

- Request Clinical Trial Authorisation (CTA) and make any amendments that are required for the authorisation
- Undertake to allow inspection of co-sponsors premises
- Gain appropriate authorisations prior to starting the trial, including authorisation from both the NHS Trust research offices and the University of Manchester, ethical approval.
  - Give notice of the following events to the appropriate regulatory bodies:
    - o amendments to CTA, make representations and amendments
      - o amendments to the protocol

- o the termination of the trial
- Maintain a Master File containing essential trial documents and to make the file available for statutory inspections by bodies such as the MHRA

Financial Responsibilities:

 Administer funding and co-ordinate any required legal agreements and investigator statements or agreements.

Responsibilities that have been delegated by DGOH & CI:

- Keep records of all adverse events reported by investigators
- Ensure recording and prompt reporting of suspected unexpected serious adverse reactions (SUSARs) to the Chief Investigator
- Ensure investigators are informed of SUSARs
- Provide an annual list of suspected adverse reactions and a safety report to the relevant authorities and committees.

# The following responsibilities are retained by the Chief Investigator, or in his absence, a named deputy(s):

• Prompt decision making as to which serious adverse events are SUSARs, and prompt reporting of that to the University of Manchester for onward reporting to the licensing authority.

# The following responsibilities are delegated by the Chief Investigator to the local Principal Investigators at each trial centre:

- Obtain Management (R&D/ Research Governance) approval
- Responsibility for putting and keeping in place arrangements to conduct the study according to Good Clinical Practice, the DH Research Governance Framework and the laws and statutes that relate to the study
- Responsibility to liaise with Pharmacy to document the supply, handling and accountability of all trial drugs
- Responsibility to ensure that all members of the study team have sufficient knowledge, training and experience to undertake the roles assigned to them and to comply with requirements as specified by the host organisation
- Responsibility to maintain a Site File (containing the essential documents) and to make the site file available for inspection if requested by the CI (on behalf of the Sponsors)
- Responsibility to conduct the study in accordance with the agreed research protocol except where
  necessary to eliminate (an) immediate hazard(s) These circumstances must be reported to the CI
  who will be responsible for reporting these events on behalf of the sponsor organisations, to the
  research ethics committee and the MHRA
- Responsibility to use all reasonable efforts to ensure that the data collected and reported are accurate, complete and identifiable at source; and that record keeping and data transfer procedures adhere to the Data Protection Act 1998
- Responsibility to supply documentation and reports as deemed necessary by the Sponsor
- Responsibility to cooperate with audits or inspections undertaken by the host institution, the Sponsors and regulatory authorities, including the MHRA as required.
- Responsibility to assist investigations into any alleged research misconduct undertaken by or on behalf of the Sponsors
- Responsibility to make the necessary local provision for archiving essential documents

The delegation of sponsorship responsibilities does not impact on or alter standard NHS indemnity cover. The agreement of delegated responsibilities is viewed as a partnership and as such it is necessary to share pertinent information between the University of Manchester and the Dudley Group of Hospitals NHS Trust/Chief Investigator, including proposed inspections by the MHRA and/or other regulatory bodies.

